9.4. Other Assessments

[REDACTED]

[REDACTED]

[REDACTED]

[REDACTED]

[REDACTED]

[REDACTED]

[REDACTED]

[REDACTED]

[REDACTED]

[REDACTED]

CONFIDENTIAL

The information contained herein may not be used, disclosed, or published without the written consent of Biogen MA Inc.

10. ADVERSE EVENTS

The definitions of an AE or SAE can be found in [Appendix 3](#).

AEs will be reported by the participant (or, when appropriate, by a caregiver or surrogate).

The Investigator and any designees are responsible for detecting, documenting, and reporting events that meet the definition of an AE or SAE and remain responsible for following up on AEs that are serious, considered related to the study treatment or the study, or that caused the participant to withdraw before completing the study.

Contacts for SAE reporting are specified in [Appendix 3](#).

10.1. Time Period and Frequency for Collecting AE and SAE Information

The collection of nonserious AE information should begin at initiation of study treatment and continue until end of study at the timepoints specified in the Schedule of Activities (Section 2).

Section 6.6 in the Investigator's Brochure represents the Reference Safety Information to determine expectedness of SAEs for expedited reporting. Following the participant's written consent to participate in the study, all SAEs, whether related or not related to study treatment, must be collected, including those thought to be associated with protocol-specified procedures.

All SAEs must be collected that occur during the screening period, continuously throughout the study, and until 30 days following the last dose (see [Table 2](#) and [Table 3](#)).

- Medical occurrences that begin before the start of study treatment but after obtaining informed consent will be recorded on the appropriate section of the electronic case report form (eCRF) section.
- All SAEs will be recorded and reported to Sponsor within 24 hours, as indicated in [Appendix 3](#).
- The Investigator will submit any updated SAE data to the Sponsor within 24 hours of this being available.
- Investigators are not obligated to actively seek AEs or SAEs in former study participants; however, if the Investigator learns of any SAE, including a death, at any time after a participant has been discharged from the study and he/she considers the event reasonably related to the study treatment or study participation, the Investigator must promptly notify the Sponsor.
- The method of evaluating and assessing causality of AEs and SAEs and the procedures for completing and reporting/transmitting SAE reports are provided in [Appendix 3](#).

10.2. Method of Detecting AEs and SAEs

AEs can be spontaneously reported or elicited during open-ended questioning, examination, or evaluation of a participant. (In order to prevent reporting bias, participants should not be questioned regarding the specific occurrence of one or more AEs.)

CONFIDENTIAL

The information contained herein may not be used, disclosed, or published without the written consent of Biogen MA Inc.

10.3. Follow-up of AEs and SAEs

Nonserious AEs should be followed to resolution or stabilization or reported as SAEs if they become serious (see [Appendix 3](#)).

Follow-up is also required for nonserious AEs that cause interruption or discontinuation of study treatment and for those present at the end of study treatment, as appropriate.

All identified nonserious AEs must be recorded and described on the nonserious AE page of the CRF (paper or electronic). Completion of supplemental CRFs may be requested for AEs and/or laboratory abnormalities that are reported/identified during the course of the study.

All SAEs will be followed until resolution, until the condition stabilizes, until the event is otherwise explained, or until the participant is lost to follow-up (as defined in Section [8.4](#)).

Further information on follow-up procedures is given in [Appendix 3](#).

10.4. Regulatory Reporting Requirements for SAEs

Prompt notification from the Investigator to the Sponsor of SAEs is essential so that legal obligations and ethical responsibilities towards the safety of participants and the safety of a product under clinical investigation are met.

An Investigator who receives an Investigator safety report describing SAEs or other specific safety information (e.g., summary or listing of SAEs) from the Sponsor will file it along with the Investigator's Brochure and will notify the IRB/IEC, if appropriate according to local requirements.

The Sponsor will be reporting AEs to regulatory authorities and ethics committees according to local applicable laws, including European Directive 2001/20/EC and Food and Drug Administration Code of Federal Regulations (CFR) 21 CFR Parts 312 and 320. A (suspected, unexpected serious adverse reaction (SUSAR) is a subset of SAEs and will be reported to the appropriate regulatory authorities and Investigators following local and global guidelines and requirements.

10.5. Pregnancy

Participants should not become pregnant or impregnate their partners for the duration of treatment with study treatment(s) BIIB092 plus 5 half-lives of study treatment BIIB092 plus 30 days for females (duration of ovulatory cycle) or 90 days for males (duration of sperm turnover) for a total of 155 days or 215 days for females and males, respectively. If a female participant becomes pregnant, study treatment must be discontinued immediately.

The Investigator must report a pregnancy occurring in a female participant by faxing or emailing the appropriate form to Biogen within 24 hours of the site staff becoming aware of the pregnancy. Refer to the Study Contact List for complete contact information. The Investigator or site staff must report the outcome of the pregnancy to Biogen. A pregnancy is not considered an AE and should not be recorded on the AE CRF.

Congenital abnormalities and birth defects in the offspring of male or female participants should be reported as an SAE if conception occurred during the study treatment period.

CONFIDENTIAL

The information contained herein may not be used, disclosed, or published without the written consent of Biogen MA Inc.

10.6. Laboratory Test Result Abnormalities

The following laboratory test result abnormalities should be captured on the nonserious AE CRF page or SAE Report Form electronic, as appropriate. Paper forms are only intended as a back-up option when the electronic system is not functioning.

- Any laboratory test result that is clinically significant or meets the definition of an SAE
- Any laboratory test result abnormality that required the participant to have study treatment discontinued or interrupted
- Any laboratory test result abnormality that required the participant to receive specific corrective therapy

It is expected that wherever possible, the clinical rather than laboratory term should be used by the reporting Investigator (e.g., anemia versus low hemoglobin value).

10.7. Potential Drug Induced Liver Injury

Potential drug induced liver injury (DILI) is defined as follows:

Aminotransaminases (ATs), including ALT or AST elevation >3 times ULN

AND

Total bilirubin >2 times ULN, without initial findings of cholestasis (elevated serum alkaline phosphatase),

AND

No other immediately apparent possible causes of AT elevation and hyperbilirubinemia, including, but not limited to, viral hepatitis, pre-existing chronic or acute liver disease, or the administration of other drug(s) known to be hepatotoxic.

All occurrences of potential DILIs, meeting the defined criteria must be reported as SAEs (see Section 10 and [Appendix 3](#) for reporting details).

10.8. Other Safety Considerations

Any significant worsening noted during interim or final physical examinations, ECG, x-ray filming, or any other potential safety assessment required or not required by protocol should also be recorded as a nonserious AE or SAE, as appropriate, and reported accordingly.

10.9. Expectedness of Events

Expectedness of all AEs will be determined by Biogen according to the Investigator's Brochure.

10.10. Suspected Unexpected Serious Adverse Reactions

SUSARs are SAEs that are unexpected and judged by the Investigator or Biogen to be related to the study treatment administered.

CONFIDENTIAL

The information contained herein may not be used, disclosed, or published without the written consent of Biogen MA Inc.

Appropriate personnel at Biogen will unblind SUSARs for the purpose of regulatory reporting. Biogen will submit SUSARs (in blinded or unblinded fashion) to regulatory agencies according to local law. Biogen will submit SUSARs to Investigators in a blinded fashion.

10.11. Overdose

An overdose is any dose of study treatment administered to a participant or taken by a participant that exceeds the dose assigned to the participant according to the protocol. Overdoses are not considered AEs and should not be recorded as an AE on the CRF; however, all overdoses must be recorded on an Overdose form and faxed or emailed to Biogen within 24 hours of the site becoming aware of the overdose. An overdose must be reported to Biogen even if the overdose does not result in an AE. If an overdose results in an AE, the AE must be recorded. If an overdose results in an SAE, both the SAE and Overdose forms must be completed and faxed or emailed to Biogen. All study treatment-related dosing information must be recorded on the dosing CRF.

10.12. Medical Emergency

In a medical emergency requiring immediate attention, site staff will apply appropriate medical intervention, according to current standards of care. The Investigator (or designee) should contact the study's Medical Director. Refer to the Study Contact List for complete contact information.

10.13. Unblinding for Medical Emergency

In a medical emergency when knowledge of the participant's treatment assignment may influence the participant's clinical care, the Investigator may access the participant's treatment assignment by IRT. The Investigator must document the reasons for unblinding in the participant's source documents. The Investigator is strongly advised not to divulge the participant's treatment assignment to any individual not directly involved in managing the medical emergency, or to personnel involved with the analysis and conduct of the study. The Investigator can contact Biogen to discuss such situations.

10.14. Deaths

Death is an outcome of an event. The event that resulted in death should be recorded on the appropriate CRF. All causes of death must be reported as SAEs within 24 hours of the site becoming aware of the event. The Investigator should make every effort to obtain and send death certificates and autopsy reports to Biogen. The term death should be reported as an SAE only if the cause of death is not known and cannot be determined.

CONFIDENTIAL

The information contained herein may not be used, disclosed, or published without the written consent of Biogen MA Inc.

11. PHARMACOKINETICS

The PK data obtained in this study will be combined with data from other studies in the clinical development program to develop a population PK model. This model will be used to evaluate the effects of intrinsic and extrinsic covariates on the PK of BIIB092 and to determine measures of individual exposure (such as steady-state trough, or time-averaged concentration, or area under the concentration-time curve). Model determined exposures will be used for exposure-response analyses of selected efficacy and safety end points. Results of population PK and exposure-response analyses will be reported separately.

Table 9 lists the sampling schedule to be followed for the assessment of pharmacokinetics in serum and CSF. Further details of blood and CSF collection and processing will be provided to the site in the procedure manual and laboratory manual.

Serum samples will be analyzed for BIIB092 using a validated ligand binding assay. Pharmacokinetic samples collected from a participant who received placebo will not be analyzed.

Table 9: Pharmacokinetic Sampling Schedule

Study Week of Sample Collection	Event	Estimated Time (Relative to start of Infusion of BIIB092) Hour: Min	BIIB092 Blood Sample for Serum	BIIB092 CSF Sample ^a
Week 0 (Day 1)	Predose	00:00	X	X
Week 0 (Day 1)	EOI ^b	01:00	X	
Week 4	Predose	00:00	X	
Week 4	EOI ^b	01:00	X	
Week 12	Predose	00:00	X	
Week 24	Predose	00:00	X	
Week 24	EOI ^b	01:00	X	
Week 36	Predose	00:00	X	
Week 48	Predose	00:00	X	
Week 48	EOI ^b	01:00	X	
Week 52	Predose	00:00	X	X
Week 56	Predose ^c	00:00	X	
Weeks 76, 100, 124, 148, 172, and 196 ^d	Predose	00:00	X	Week 100 only

CSF = cerebrospinal fluid; EOI = end of infusion.

^a Collect at the time of LP ()

CONFIDENTIAL

The information contained herein may not be used, disclosed, or published without the written consent of Biogen MA Inc.

- ^b This sample should be taken immediately prior to stopping the infusion (preferably within 2 minutes prior to the end of the infusion). If the end of infusion is delayed to more than the nominal infusion duration, the collection of this sample should also be delayed accordingly.
- ^c The scheduled predose sampling at Week 56 is also the Week 52 postdose sampling (672 hours after Week 52 dosing).
- ^d Visit intervals of 24 weeks after Week 52 (Weeks 76, 100, 124, 148, 172, and 196).

CONFIDENTIAL

The information contained herein may not be used, disclosed, or published without the written consent of Biogen MA Inc.

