5.6. Scientific Rationale for Study Design

The double-blind period of the study is intended to determine the efficacy and safety/tolerability of BIIB092. It is anticipated that participants will be randomized in a 2:1 ratio to receive 2000 mg of BIIB092 or placebo, respectively, administered by IV infusion once Q4W for approximately 48 weeks (up to a total of 13 times). The justification for the dose is described in Section 5.7 and based on previous studies evaluating the PK of BIIB092 and PD effects on unbound N-terminal tau levels in CSF. A duration of treatment of up to 52 weeks and comparison with a placebo control are considered adequate and appropriate to evaluate the efficacy of BIIB092 on the primary and secondary endpoints, given the natural history of PSP and the lack of any approved therapies.

The open-label extension period of the study is intended to further characterize the long-term efficacy and safety/tolerability of BIIB092. It is anticipated that all participants in the study, including those randomized to receive placebo in the double-blind period, will receive 2000 mg of BIIB092 administered Q4W by IV infusion throughout the open-label extension period of the study.

CONFIDENTIAL

The information contained herein may not be used, disclosed, or published without the written consent of Biogen MA Inc.

The QMA substudy in the open-label extension period is intended to further characterize disease progression with wearable sensors. Postural instability, gait disturbances, and falls are prominent signs of PSP that impact participant outcomes. At present these signs are assessed in the clinic with questionnaires. It is anticipated that advances in wearable sensor technology and analytics could improve quantification of these signs and may provide sensitive measures of disease progression.

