7.3. Blinding

Blinding of treatment assignment is critical to the integrity of this clinical study. However, in the event of a medical emergency or pregnancy in an individual participant in which knowledge of the investigational product is critical to the participant's management, the blind for that participant may be broken by the Investigator. The participant's safety takes priority over any other considerations in determining if a treatment assignment should be unblinded.

Before breaking the blind of an individual participant's treatment, the Investigator should determine that the unblinded information is necessary, i.e., that it will alter the participant's immediate management. In many cases, particularly when the emergency is clearly not related to the IP, the problem may be properly managed by assuming that the participant is receiving active product. It is highly desirable that the decision to unblind treatment assignment be discussed with the Medical Monitor, but the Investigator always has ultimate authority for the decision to unblind. The Principal Investigator should only call in for emergency unblinding AFTER the participant has made the decision to discontinue from study treatment.

For information on how to unblind in an emergency, consult the IRT manual.

CONFIDENTIAL

The information contained herein may not be used, disclosed, or published without the written consent of Biogen MA Inc.

In cases of accidental unblinding, contact the Medical Monitor and ensure every attempt is made to preserve the blind. The Bioanalytical Sciences section or its designate will be unblinded to the randomized treatment assignments in order to minimize unnecessary analysis of samples from control group participants.

Any request to unblind a participant for non-emergency purposes should be discussed with the Medical Monitor.

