3.2 Population

- Dosed subjects: enrolled subjects who received at least one dose of study therapy, i.e., blinded therapy (BIIB092 or placebo) or open-label BIIB092. This is the same as the “Treated participants” in Section 17.2 of the protocol.
- Intent-to-treat (ITT) population:
The intent-to-treat population is defined as all randomized subjects who received at least one dose of blinded study treatment (BIIB092 or placebo).
- Safety population: all randomized subjects who received at least one dose of study treatment (BIIB092 or placebo).
- Efficacy MRI population: the subset of the ITT population who had a least one measurable brain volumetric measurement.
- Safety MRI population: the subset of the safety population who had a least one post-baseline safety MRI.
- Serum PK analysis population: the subset of the safety population who had at least one measurable post-baseline BIIB092 concentration in serum.

- CSF PK analysis population: the subset of the safety population who had at least one measurable post-baseline BIIB092 concentration in CSF.
- CSF PD analysis population: the subset of the safety population who had both baseline and at least one measurable post-baseline N -terminal tau CSF sample.
- Anti-drug antibody (ADA) analysis population: the subset of the safety population who had at least one post-dose sample evaluable for ADA.

OLE treatment groups for analyses

Analyses for efficacy data will be displayed by the following treatment groups according to randomization assignment at the start of the placebo-controlled period:

- BIIB092 early start: subjects who are assigned to (1) receive BIIB092 in the placebo-controlled period and (2) continue receiving BIIB092 in the OLE period
- BIIB092 late start: subjects who are assigned to (1) receive placebo in the placebo-controlled period and (2) switch to BIIB092 in the OLE period

Unless otherwise specified, analyses for safety, PK, and ADA data will be displayed by the following treatment groups according to dose received:

- BIIB092 early start: subjects who receive BIIB092 in the placebo-controlled period (regardless of randomization assignment)
- BIIB092 late start: subjects who receive only placebo in the placebo-controlled period (regardless of randomization assignment) and switch to receive BIIB092 in the OLE period
- BIIB092 total: subjects in either BIIB092 early or late start treatment groups

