7.11 Serum Pharmacokinetics

The PK Population will be used for all listings, summaries, and statistical analyses. Analysis will include all valid data in the PK dataset for BIIB092 in the active treatment (placebo-controlled and OLE) period.

In this study, additional samples for serum PK, referred to as “event driven” samples, may be collected for subjects with hypersensitivity events. Data from these samples will be considered part of a subject’s overall serum PK assessment.

Subject serum BIIB092 concentrations will be listed and summarized by treatment group and visit.

The individual serum PK parameter C_{trough} will be listed for BIIB092 including any exclusions and reasons for exclusions. Summary statistics will be tabulated by treatment group and visit. Plots of individual C_{trough} over time may be provided. Overlays of individual C_{trough} over time may be provided by treatment. Plots of mean (+ SE) C_{trough} versus time will be presented by treatment group. Geometric means and coefficients of variation will also be presented for C_{trough} .

geometric %CV, median, minimum, and maximum) for serum concentrations, BLQ value pre day 1 of study treatment will be set to 0, all post first dose of study treatment BLQ values will be set to half the LLOQ value. Mean serum concentrations that are BLQ will be presented as BLQ, and the SD and %CV will be reported as not applicable. Summary statistics of the serum concentrations will be tabulated by group, day, and scheduled time point. At the discretion of the pharmacokineticist and/or biostatistician, samples may be excluded from descriptive statistics if there are large deviations between scheduled and actual sampling times, or large deviations between actual dose and nominal dose.

Mean (\pm SE) serum concentration vs. time (scheduled) profiles for the treatment group will be presented graphically on linear and semilogarithmic scales. Serum concentration vs. time (actual) profiles from Day 1 to Week 100, for each subject, may be provided. Samples may be excluded from the mean plots if there are large deviations between scheduled and actual sampling times, or large deviations between actual dose and nominal dose.

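### The rule against analysing PK samples from placebo participants has no period limit, so read literally it covers their samples after the Week 52 switch to BIIB092 and contradicts the extension SAP

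*Protocol*

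**What the plan says.** Protocol Section 11 closes its description of the serum assay with the rule "Pharmacokinetic samples collected from a participant who received placebo will not be analyzed". It gives no period and no exception. Section 7.3 (Blinding) unblinds the bioanalytical group to the randomised assignments "in order to minimize unnecessary analysis of samples from control group participants", also with no period stated.

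According to Section 5.6 of the protocol, everyone in the extension, "including those randomized to receive placebo in the double-blind period, will receive 2000 mg of BIIB092", at the same interval as before. The Synopsis and Section 5.1.1 put the first open-label dose at Week 52. Table 9 in Section 11 schedules predose serum at Weeks 56, 76, 100, 124, 148, 172 and 196. Its footnote identifies the Week 56 sample as the one taken 672 hours after the Week 52 dose.

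The extension SAP (Section 3.2, Population) displays PK by early start, late start and total. It defines late start as "subjects who receive only placebo in the placebo-controlled period (regardless of randomization assignment) and switch to receive BIIB092 in the OLE period". The Analysis Period section takes late-start data from the extension only. Section 7.11 then says: "Subject serum BIIB092 concentrations will be listed and summarized by treatment group and visit". It also requires trough summaries and mean trough plots by group. Entry to the serum PK population requires at least one measurable post-baseline serum concentration.

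**The concern.** The rule selects by participant, not by what the participant was receiving when the sample was drawn. Every late-start participant has received placebo by definition, so every one of them meets the exclusion. If their extension samples are not assayed, none can enter the serum PK population, and the late-start column in the extension PK tables is empty.

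For these participants the Week 56 sample is the trough after a first BIIB092 dose. The same data are meant to feed the population PK and exposure-response models in Section 11. Protocol Section 14 also says that drug-exposure data from event-driven samples, taken after hypersensitivity reactions of Grade 3 or higher, will be reported. The literal rule would bar assay of such a sample from a late-start participant.

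**Working it through.** This is mainly a comparison of texts, with arithmetic only for scale.

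**Texts side by side**

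1. Section 11 excludes the PK samples of any participant who received placebo, at any time.
2. A late-start participant received only placebo in the double-blind period, so rule 1 covers all of that participant's samples, including those drawn on BIIB092.
3. Table 9 schedules extension serum without separating former placebo participants from the rest.
4. The extension SAP tabulates late-start serum concentrations and troughs, using extension data.
5. An unassayed sample gives no measurable concentration, so under rule 1 the late-start group in step 4 has no members.
6. Nothing in the protocol or either SAP exempts samples drawn after the switch.

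Steps 1 and 4 cannot both be followed as written.

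**Scale**

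Inputs are 153 randomised to placebo and 459 in total, with 25% dropout (protocol Section 17.1), and the extension time points in Table 9.

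- Plan's own figures: 153 × 0.75 = 114.75, stated as 115. 459 × 0.75 = 344.25, stated as 345 (230 + 115). These reproduce apart from rounding.
- Share of expected completers: 115 / 345 = 33%.
- Scheduled serum samples after the switch: Weeks 56, 76, 100, 124, 148, 172 and 196, which is 7 per participant.
- Ceiling: 115 × 7 = 805. This needs every placebo completer to enter the extension and reach Week 196.

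The documents give neither uptake nor duration, so the following are assumptions that show the range:

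| Assumption | Samples |
|---|---|
| 100% enter and reach Week 196 | 115 × 7 = 805 |
| 75% enter and reach Week 196 | 86 × 7 = 602 |
| 50% enter and reach Week 196 | 58 × 7 = 406 |
| All 115 enter, 25% per year then leave | about 557 |

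The last row sums 0.75^(w/52) over w = 4, 24, 48, 72, 96, 120 and 144 weeks after the switch. The sum is 0.978 + 0.876 + 0.767 + 0.671 + 0.588 + 0.515 + 0.451 = 4.846, and 115 × 4.846 = 557.

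The extension SAP is written for an interim analysis. Its Sections 5.3 and 7.10 say that too few participants will have reached Week 100 by then. For those tables, late-start participants would contribute mainly Weeks 56 and 76, at most 115 × 2 = 230 samples.

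**The case against.** The strongest reply is that the intent is clear. Section 7.3 speaks of minimising unnecessary analysis of control-group samples. From Week 52 there is no control group, and an assay from someone on BIIB092 is not unnecessary. Protocol Section 17.5.1 leaves PK analyses to the SAP, and the SAP includes late-start participants. On this view the defect is one loose sentence that no competent laboratory would apply against Table 9.

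Much of this stands. The intent probably is to skip samples drawn on placebo, and Section 7.3 is softer than Section 11: it limits assays and does not forbid them. A reader might infer that the plan discards the extension samples, or that the late-start tables cannot be produced. The documents do not support that. Section 11 says the samples will not be analysed, not that they will be destroyed, and the laboratory's working instructions are not in the documents.

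Three further inferences also go too far:

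- 805 is not an expected loss. It is a ceiling that needs full uptake and follow-up to Week 196.
- The association of anti-drug antibodies with PK is not a required output. Extension SAP Section 8 says only that it may be explored. Individual trough plots are likewise optional, while the mean plots are firm.
- The Week 52 predose sample of a former placebo participant need not be assayed as a baseline. It precedes any BIIB092, and Section 7.11 plans no change-from-baseline PK analysis.

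What does not stand is the claim that intent makes the wording harmless. The assignment given to the bioanalytical group is the randomised one, and it stays placebo after Week 52. A sample selection built on it exactly as Section 11 reads would omit these samples without anyone having decided to omit them.

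**Conclusion.** The rule in Section 11 is wrong as written and conflicts with both Table 9 and the extension SAP. It is more than a missing detail, but it is most likely a wording error and not a deliberate analysis choice. Any actual loss depends on the laboratory following the sentence literally.

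If it did, up to about 115 participants would have no extension PK data, with up to 7 scheduled serum samples each. The one-third share is of expected completers and assumes that all placebo completers enter the extension.

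The conflict in the planned interim tables concerns serum only, because CSF PK is not run at that interim. The protocol rule would also cover Week 100 CSF samples. The double-blind efficacy and safety analyses and the sample size do not depend on these samples.

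**What to change.** Replace the Section 11 sentence with: *Pharmacokinetic samples collected before the first BIIB092 dose from participants randomized to placebo will not be analyzed; samples collected after a participant's first BIIB092 dose will be analyzed.*

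Amend Section 7.3 so that the control-group samples it refers to are those drawn before the first BIIB092 dose. Then confirm that the laboratory's sample selection uses that date and not the randomised arm alone. No exception is needed for the Week 52 predose sample.

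The cost is two protocol sentences and one check with the laboratory. There are no new visits or samples: Table 9 already schedules the collection, and the extension SAP tables already presuppose the assays.
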